**NCT ID not yet assigned**

**Document Date: 10.01.2022**

## RESEARCH PROTOCOL

NAME OF THE RESEARCH:	Evaluation of Clinical and Radiological Success of the Platelet-Rich Fibrin, Chitosan and Blood Clot as a Scaffold in the Regenerative Endodontic Treatment of Molar Teeth
CENTER/CENTERS WHERE THE STUDY WILL BE DONE	Inonu University Faculty of Dentistry Department of Pedodontics
BASIS AND JUSTIFICATION OF THE RESEARCH:	Young permanent teeth may become necrotic due to caries or trauma. Root development stops in necrotic teeth, resulting in thin root dentin walls and an open apex. Therefore, appropriate mechanical preparation and subsequent hermetic filling during endodontic treatment becomes difficult, and root canal treatment cannot be performed. Calcium hydroxide apexification and single-session apexification techniques are frequently used, but they cannot ensure continued root development. Teeth with these techniques are prone to fracture due to thin root canal walls. Thus, regenerative endodontic treatments, which provide pulp regeneration, dentin formation, and continued root development after treatment, have become widespread. The terms regenerative endodontics, revascularization, and revitalization have been adopted in the literature. Regenerative endodontics aims to promote continued root maturation by restoring the pulp-dentin complex. (1) A fundamental component of regenerative endodontic treatment is the presence of a scaffold that allows for the adhesion, proliferation, and differentiation of stem cells from the apical papilla. Many studies in the literature have examined various scaffold materials used in regenerative endodontic treatment and compared their success. These studies support the idea that an ideal scaffold material should support the survival and proliferation of apical papilla stem cells, be biocompatible, allow cell migration and vascularization, be biodegradable, and be nontoxic. Several studies have determined that, in the absence of a scaffold, apical papilla stem cells do not adhere to the root canal system and therefore fail to regenerate the pulp-dentin complex (2, 3, 4).

	
Although PRF and blood clots are widely used and will be used in this study, chitosan is an important alternative regenerative endodontic treatment material that has achieved successful results in recent years (2). Although there are studies evaluating these three materials together and separately, there are no studies evaluating their clinical and radiological success in molar teeth. Controlled clinical studies are needed, particularly for molar teeth.
 
 
1. Lin, Louis M, and Bill Kahler. "A review of regenerative endodontics: current protocols and future directions." Journal of Istanbul University Faculty of Dentistry vol. 51,3 Suppl 1 S41-S51. 2 Dec. 2017, doi:10.17096/jiufd.53911
 
2. Raddall, Gavin et al. "Biomaterials and Scaffold Design Strategies for Regenerative Endodontic Therapy." Frontiers in bioengineering and biotechnology vol. 7 317. 15 Nov. 2019, doi:10.3389/fbioe.2019.00317
 
3. Trevino, Ernesto G et al. "Effect of irrigants on the survival of human stem cells of the apical papilla in a platelet-rich plasma scaffold in human root tips." Journal of endodontics vol. 37,8 (2011): 1109-15. doi:10.1016/j.joen.2011.05.013.
 
4. Jadhav, Ganesh et al. "Revascularization with and without platelet-rich plasma in nonvital, immature, anterior teeth: a pilot clinical study." Journal of endodontics vol. 38,12 (2012): 1581-7. doi:10.1016/j.joen.2012.09.010
 

--	---

AIM OF THE RESEARCH	
This study aimed to evaluate and compare, both clinically and radiographically, the treatment and long-term follow-up results of using platelet-rich fibrin, blood clots, and chitosan as scaffolds in molar tooth regeneration.

----------------------------	---

RESEARCH METHOD:	
The sample group for the planned study will be selected from among patients applying to the Inonu University Faculty of Dentistry Pedodontics Clinic with necrotic pulp and immature apices. Block randomization will be used to determine the material to be applied to the teeth. According to the minimum sample size determined by the power analysis, the study will be conducted on at least 24 teeth. Patients who leave the study early or do not comply with the treatment procedure will be excluded, and new patients will be added in their place. Patients will not undergo additional procedures, appointments, or radiograph requests within the scope of the study. Regeneration treatment is a popular, routinely applied procedure in our clinic and in dentistry faculties. It is also successfully performed by pedodontists and endodontists in private clinics. The protocol stipulates that each study participant will be informed about the nature of the treatment to be administered and the research to be

-------------------------	---

conducted. Informed consent will be obtained from the patient's legal guardian. In the initial session, local anesthesia will be administered to the teeth, a rubber dam will be positioned, and the caries will be meticulously removed. Subsequently, the pulp will be meticulously eradicated through the employment of a sterile barnacle. Each canal will undergo irrigation with 20 milliliters of a 2.5% sodium hypochlorite solution. Subsequently, a volume of 20 milliliters of sterile saline will be applied to each canal. Calcium hydroxide paste will be placed as a medicament in the canals that have been dried with paper points and closed with a temporary filling. The patient will be contacted to schedule a second session between one and four weeks later. In the second session, local anesthesia will be administered without the use of a vasoconstrictor. Prior to this, a rubber dam will be placed, and the temporary filling will be removed. The calcium hydroxide paste placed in the canal as a medicament will be removed, and each canal will undergo a gentle irrigation with 20 milliliters of 17% ethylenediaminetetraacetic acid (EDTA). The canals will be dried using paper points. The induction of bleeding will be accomplished through the utilization of an excessive number of instruments, specifically a 20 number K File, which will be inserted 2 mm beyond the apical extent of the canal. Subsequently, platelet-rich fibrin or chitosan (Sigma-Aldrich) will be placed in the canal as a scaffold. In the "control group," where apical bleeding will be used directly as a scaffold, which is mentioned as the gold standard in the literature because it is the most easily accessible material, these will not be used and only bleeding from the apex will be sufficient. MTA (Angelus MTA) will be applied to the canal orifices to prevent oral fluids from leaking into the canal. The MTA will be covered with glass ionomer cement. Dental elements that are deemed suitable for endodontic restoration will undergo treatment with composite fillings. Teeth that are not amenable to restoration with composite fillings due to extensive material loss can be restored with stainless steel crowns. The protocol stipulates that patients are to be contacted for medical checkups at three-month intervals during the first year of the study, and at six-month intervals during the second year. The evaluation of the data will be conducted with the utilization of statistical software and the expertise of subject matter specialists. During the check-ups, the teeth will be evaluated according to the criteria listed below.

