
**A- CLINICAL**

1. Loss of Tooth
2. Presence of pain

	
 
3. Percussion and Palpation Sensitivity
 
4. Presence of Pathological Mobility
 
5. Presence of fistula
 
6. Evaluation of restoration
 
 
B- RADIOGRAPHIC
 
 
1. Pulp Obliteration
 
2. Internal - External Root Resorption
 
3. Apical Radiolucency
 
4. Increase - Decrease in Lamina Dura Width
 
5. Presence of Ankylosis
 
6. Root length
 
7. Root thickness
 

--	--

POWER ANALYSIS:	
The number of people in the study was decided by a calculation called "power analysis." The G*power 3.1 program was used to calculate the sample size. The sample size was determined to be 24, with 8 teeth for each group. The effect size was set at 0.25, the margin of error at 0.05, the confidence level at 0.95, and the universe representation power at 0.95 Cohen states that the sample size for which power values ranging from 0.90 to 0.99 were calculated should be reached (5).
 
5. Cohen, J, (1988), Statistical Power Analysis for the behavioral sciences, 2. Edition, Taylor & Francis INC, New York, US.)

------------------------	--

END POINT OF THE RESEARCH	
The goal of this study is to follow patients over time to see if regeneration treatment works for molar teeth with open apex. We will use three different scaffolds for the treatment. No clinical controlled study has been found in the literature on regeneration with molar teeth. The existing data are in the form of case reports or studies performed on incisors. The goal of the study is to successfully obtain 12-18 months of clinical and radiographic follow-up with at least 24 teeth. We will compare the success rates of the materials used based on the data we get. Since scientists haven't found the perfect material yet, this study will be a big help to researchers when it's finished.

----------------------------------	---

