**NCT ID not yet assigned**

**Last updated: 10.01.2022**

## **Study Design and Statistical Analysis Plan**

This study was designed as a randomized, controlled, single-blind prospective clinical trial. The minimum required sample size was calculated using G\*Power Version 3.1.9.4. Assuming a confidence level of 95% (1- $\alpha$ ), a power of 80% (1- $\beta$ ), and an effect size of  $d = 0.7$ , the total required sample size for comparing three independent groups was calculated as 24, with 8 teeth in each group.

Data were analyzed using IBM SPSS Statistics Version 23 and R software. The Shapiro–Wilk test was employed to assess the normality of the data distribution. For comparisons involving three or more groups with normally distributed data, one-way analysis of variance (ANOVA) was conducted. In cases where the data did not follow a normal distribution, the Kruskal–Wallis H test was applied for comparisons across three or more groups.

Robust regression analysis was conducted to identify independent variables affecting non-normally distributed outcomes. The Fisher–Freeman–Halton test was used to examine associations between categorical variables. Inter-observer agreement was assessed using the intraclass correlation coefficient (ICC). Descriptive statistics are presented as frequencies and percentages for categorical variables; and as mean  $\pm$  standard deviation, median (minimum–maximum), or median (25th–75th percentile) for continuous variables, depending on the distribution. A p-value of  $<0.05$  was considered statistically significant.

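### Early leavers and non-compliers are excluded and replaced with no time limit and no defined analysis set, so success rates are biased if leaving or non-compliance is related to outcome

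*Protocol*

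**What the plan says.** The Protocol allocates by block: "Block randomization will be used to determine the material to be applied to the teeth". The SAP confirms the design: "This study was designed as a randomized, controlled, single-blind prospective clinical trial". Under RESEARCH METHOD the Protocol then says: "Patients who leave the study early or do not comply with the treatment procedure will be excluded, and new patients will be added". Neither document defines leaving early or complying, sets a cut-off time, or says how a replacement is allocated or when randomisation takes place.

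Treatment takes two sessions, with the scaffold placed at the second: "The patient will be contacted to schedule a second session between one and four weeks later". Follow-up is long: "patients are to be contacted for medical checkups at three-month intervals during the first year of the study", then every six months in the second year.

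Under END POINT OF THE RESEARCH the target is counted in teeth followed up: "The goal of the study is to successfully obtain 12-18 months of clinical and radiographic follow-up with at least 24 teeth". The comparison of interest is "We will compare the success rates of the materials used based on the data we get". For categorical data the SAP states: "The Fisher–Freeman–Halton test was used to examine associations between categorical variables". It names no analysis set, missing-data method or sensitivity analysis.

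**The concern.** Randomisation makes the three groups comparable at allocation. A rule that removes teeth afterwards, for reasons that may depend on how the tooth is doing, can undo that. Tooth loss, pain and fistula are among the Protocol's evaluation criteria, and such events could affect whether a family returns. A family whose child has no symptoms may also stop coming. The first pushes the completers' success rate up, the second pushes it down.

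The two limbs of the rule differ in weight. Non-compliance with the two-session treatment may fall mostly before the scaffold is placed, where loss does less harm if the material is not yet known. Leaving early can happen at any time in follow-up, after the material is in place and outcomes have been seen, so it is the stronger limb.

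The comparison of success rates is what the trial is for. If excluded teeth are not kept and reported by arm, a reader could not check afterwards whether the rule changed the answer.

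**Working it through.** **Inputs.** From the documents: three arms of 8 teeth (24 in total), significance at p < 0.05, and the Fisher–Freeman–Halton test. The SAP's 24 reproduces from a one-way ANOVA with 0.7 read as Cohen's f, alpha 0.05 and power 80% (power at 24 teeth: 0.822). Nothing below depends on that calculation. The documents give no success or loss rates, so all those used here are assumptions.

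**1. Success rate among completers.** Let p be true success, s the share of successes that leave and f the share of failures that leave. Completers show p(1−s) / [p(1−s) + (1−p)(1−f)]. At p = 0.80:

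- s = 5%, f = 5%: 0.76 / (0.76 + 0.19) = 80.0%, no bias
- s = 5%, f = 25%: 0.76 / (0.76 + 0.15) = 83.5%
- s = 5%, f = 50%: 0.76 / (0.76 + 0.10) = 88.4%
- s = 25%, f = 5%: 0.60 / (0.60 + 0.19) = 75.9%

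The same four cases give 70.0%, 74.7%, 81.6% and 64.8% at p = 0.70, and 90.0%, 91.9%, 94.5% and 87.7% at p = 0.90.

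**2. Contrast between arms.** With equal true success and the same leaving pattern in every arm, all arms shift together and no false difference appears. If two arms both truly succeed in 75%, 10% of successes leave in each, but 50% of failures leave in one and 10% in the other, the first reads 0.675 / (0.675 + 0.125) = 84.4% and the second 75.0%. That is a false difference of 9.4 points.

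**3. Effect of one tooth on the test.** Exact Fisher–Freeman–Halton p-values, with one excluded failure put back:

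- 8/8, 8/8, 5/8: 168/2024 = 0.083. It becomes 8/8, 8/8, 5/9: 266/12650 = 0.021.
- 8/8, 7/8, 3/8: 2772/134596 = 0.021. It becomes 8/9, 7/8, 3/8: 32476/480700 = 0.068.

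These are chosen boundary tables. To see how often it matters, I enumerated all 9 × 9 × 9 = 729 possible results, weighted them by binomial probability, and added one failure to an arm picked at random. Significance changes in 2.7%, 2.1% or 0.9% of results when all arms succeed at 70%, 80% or 90%. At 90%, 90% and 50% it changes in 11.5%, or 17.7% if arms are weighted by their failure probability.

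**4. Choice of replacement estimate.** Keeping recorded failures while dropping teeth that leave without one is not neutral. If failures are recorded before leaving and the loss is unrelated to outcome, a true 80% reads 0.80(1−s) / [0.80(1−s) + 0.20]. For losses of 5%, 10%, 20% and 30% that is 79.2%, 78.3%, 76.2% and 73.7%, where completers alone read 80.0%. A Kaplan-Meier estimate gives such teeth credit up to their last visit and avoids this bias when leaving is unrelated to outcome.

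**5. Bounds.** If failures leave unseen, counting all leavers as failures gives p(1−s), and counting all as successes gives p + (1−p)f. For the three unequal cases at p = 0.80 the ranges are 76.0–85.0%, 76.0–90.0% and 60.0–81.0%. Each contains the true 80%.

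**The case against.** Part of the reading is inference. 'Excluded' could mean withdrawn from further visits with the data kept. The target of 24 followed-up teeth is a goal, not an analysis population, and comparing success on the data obtained does not say that leavers' data are discarded. This stands as far as intent goes, but no sentence in either document says the data are kept, or that a failure recorded before leaving still counts.

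Every rate above is assumed, so the size of any bias is unknown. That stands.

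A reader might infer that the rule will make the success rates look too good, or will favour one scaffold. The documents support neither: the bias can go either way, is zero if leaving is unrelated to outcome, and yields no false contrast when true success and leaving pattern are the same in every arm.

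A reader might also infer from the boundary tables that one tooth usually decides significance. It does not. Counting a result as changed if adding a failure to any one of the three arms would change it gives 7%, 6%, 3% and 33%. That in effect picks the most sensitive arm afterwards, whereas one excluded failure belongs to one arm. The figures in step 3 are the fair ones. Even they presuppose that a failure was excluded, so they show fragility and do not predict error.

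**Conclusion.** The concern holds for the open-ended exclusion and replacement rule and the missing analysis set, with high confidence, and it should be fixed before analysis. The rule decides which teeth enter every comparison. Its effect depends on whether leaving or non-compliance is related to outcome, and on whether that relation differs by arm. Under the assumed losses, a true 80% reads anywhere from 75.9% to 88.4%. These are illustrations, not estimates for this trial. If the sponsor always meant to keep the data of leavers, a short paragraph settles it.

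**What to change.** Replace the sentence in the Protocol and put the same text in the SAP:

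> All randomised teeth that receive a scaffold (including the induced clot in the control group) are analysed in the group to which they were randomised. Non-compliance is recorded but is not a reason for exclusion. Teeth that leave before scaffold placement are not in the main analysis and are reported by arm with the reason; a sensitivity analysis counts them as failures. A failure recorded at any visit counts as a failure even if the patient later leaves. The main success rate is the Kaplan-Meier estimate at the final planned visit, with teeth that leave without a recorded failure censored at their last attended visit. Two sensitivity analyses count all such teeth, in every arm, as failures and as successes. Exclusions and losses are reported by arm with reason and time. An added tooth takes the next number on the block-randomisation list and is analysed in addition to, not instead of, the tooth that left.

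The SAP must first state which of the Protocol's clinical and radiographic criteria make a tooth a failure; neither document does so now. It must also name one visit as final, since the Protocol mentions both 12–18 months and check-ups through the second year, and name a test to accompany the Kaplan-Meier rates. The Fisher–Freeman–Halton test can serve for the two sensitivity analyses.

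Cost: wording, a little more analysis work, and success rates with wider and possibly less favourable stated uncertainty. No visits or procedures are added. The Kaplan-Meier rate is still biased if leaving is related to an unseen outcome, which is why the two bounds are reported beside it.

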
**A- CLINICAL**

1. Loss of Tooth
2. Presence of pain

	
 
3. Percussion and Palpation Sensitivity
 
4. Presence of Pathological Mobility
 
5. Presence of fistula
 
6. Evaluation of restoration
 
 
B- RADIOGRAPHIC
 
 
1. Pulp Obliteration
 
2. Internal - External Root Resorption
 
3. Apical Radiolucency
 
4. Increase - Decrease in Lamina Dura Width
 
5. Presence of Ankylosis
 
6. Root length
 
7. Root thickness
 

--	--

POWER ANALYSIS:	
The number of people in the study was decided by a calculation called "power analysis." The G*power 3.1 program was used to calculate the sample size. The sample size was determined to be 24, with 8 teeth for each group. The effect size was set at 0.25, the margin of error at 0.05, the confidence level at 0.95, and the universe representation power at 0.95 Cohen states that the sample size for which power values ranging from 0.90 to 0.99 were calculated should be reached (5).
 
5. Cohen, J, (1988), Statistical Power Analysis for the behavioral sciences, 2. Edition, Taylor & Francis INC, New York, US.)

------------------------	--

END POINT OF THE RESEARCH	
The goal of this study is to follow patients over time to see if regeneration treatment works for molar teeth with open apex. We will use three different scaffolds for the treatment. No clinical controlled study has been found in the literature on regeneration with molar teeth. The existing data are in the form of case reports or studies performed on incisors. The goal of the study is to successfully obtain 12-18 months of clinical and radiographic follow-up with at least 24 teeth. We will compare the success rates of the materials used based on the data we get. Since scientists haven't found the perfect material yet, this study will be a big help to researchers when it's finished.

----------------------------------	---

EXPECTED BENEFITS AT THE END OF THE RESEARCH	
The goal is to compare the long-term success of chitosan, a material that has been proven to work in clinical trials, with other materials. This will provide useful data for the scientific literature. Chitosan is used a lot in dentistry because it kills bacteria and helps tissue grow. (6). Studies have shown that it has some benefits. It is a good support structure for a type of tooth cell called apical papilla stem cells. It is also compatible with living tissue and is not very toxic. However, there is limited information about the use of chitosan in literature about other teeth. Since the roots are thin in molars, it is quite difficult to perform root canal treatment with apical plug. Therefore, the regenerative endodontic procedure was developed as an alternative, which is quite advantageous in molars with open apicals. Since many patients come from nearby provinces, the number of molars that need a regenerative endodontic treatment is also increasing in our clinic, where we see a lot of patients. This study aims to provide valuable data to the existing literature by evaluating molar teeth. Comparison of 3 different scaffold materials will contribute to the determination of materials that are advantageous in terms of cost/benefit ratio and will provide support for their clinical use.
 
6) Fakhri, Elaheh et al. "Chitosan biomaterials application in dentistry." International journal of biological macromolecules vol. 162 (2020): 956-974. doi:10.1016/j.ijbiomac.2020.06.211
 
7) Chang, Bei et al. "Injectable scaffolds: Preparation and application in dental and craniofacial regeneration." Materials science & engineering. R, Reports : a review journal vol. 111 (2017): 1-26. doi:10.1016/j.mser.2016.11.001

---	--

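### The protocol and SAP justify the same 24 teeth with different power inputs, and the protocol's 95% power does not apply to the planned one-way ANOVA (16% if 0.25 is Cohen's f)

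*Protocol*

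**What the plan says.** **Protocol, Power Analysis.** The total is 24 teeth, 8 in each of three groups, calculated in G*Power 3.1 with "effect size was set at 0.25, the margin of error at 0.05, the confidence level at 0.95, and the universe representation power at 0.95". No statistical test, effect-size metric or outcome is named. The section then sets a target for power: "Cohen states that the sample size for which power values ranging from 0.90 to 0.99 were calculated should be reached".

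**Protocol, Research Method.** The enrolment minimum rests on this calculation: "According to the minimum sample size determined by the power analysis, the study will be conducted on at least 24 teeth".

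**SAP, Study Design and Statistical Analysis Plan.** With 95% confidence, 80% power and d = 0.7 in G*Power 3.1.9.4, "the total required sample size for comparing three independent groups was calculated as 24, with 8 teeth in each group". No outcome is named here either. For the analysis itself: "For comparisons involving three or more groups with normally distributed data, one-way analysis of variance (ANOVA) was conducted". The Kruskal-Wallis test is the fallback ("In cases where the data did not follow a normal distribution"). No repeated-measures analysis is planned.

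Both documents carry the date 10.01.2022.

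**The concern.** The two documents tell the reader different things about what 24 teeth can detect, and the identical dates leave no way to decide which statement governs. The SAP's 80% also falls below the 0.90 to 0.99 range that the protocol says should be reached.

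The practical risk lies in interpreting the result. Someone who takes the protocol at its word would think an effect of 0.25 has a 95% chance of being detected. If the planned ANOVA has far less power than that, a non-significant comparison of the three scaffolds would be taken as much stronger evidence of no difference than it is.

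**Working it through.** **Inputs.** Three groups, N = 24, 8 per group (both documents). Alpha 0.05 (both). Protocol: effect size 0.25, power 0.95. SAP: effect size 0.7, power 0.80. Test: the SAP's one-way ANOVA.

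**Formula.** Power is the probability that a noncentral F variable with df1 = 2, df2 = N − 3 and noncentrality λ = N·f² exceeds the 5% critical value. At N = 24, df2 = 21 and the critical value is 3.47. Sample sizes below are the smallest balanced totals.

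**1. The SAP's figure.** Read 0.7 as Cohen's f: λ = 24 × 0.49 = 11.76, power 82.2%. At N = 21 power is 75.4%, so 24 is the smallest balanced total reaching 80%. The figure reproduces.

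Read 0.7 as a literal Cohen's d between the two extreme groups and it does not:

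| Conversion of d = 0.7 | f | Power at N = 24 |
|---|---|---|
| middle mean at the midpoint | 0.286 | 19.7% |
| middle mean at one extreme | 0.330 | 25.1% |
| f = d/2 | 0.350 | 27.8% |

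So d is probably a mislabel for f. This is not certain: a group-by-time test with f = 0.35, 2 measurements and an assumed correlation of 0.5 also gives 82.2% at 24 and 75.4% at 21.

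**2. The protocol's figure in the same ANOVA.** The metric is not stated, so the range of readings is shown:

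| Reading of 0.25 | f | λ = 24·f² | Power at N = 24 |
|---|---|---|---|
| Cohen's f | 0.25 | 1.5 | 16.0% |
| f-squared | 0.50 | 6.0 | 52.0% |
| eta-squared, f = √(0.25/0.75) | 0.577 | 8.0 | 65.0% |

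None approaches 95%.

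**3. What each effect size requires, and what 24 teeth can detect.**

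| | 80% power | 90% power | 95% power |
|---|---|---|---|
| N needed at f = 0.25 | 159 | 207 | 252 |
| N needed at f = 0.70 | 24 | 30 | 36 |
| Smallest f at N = 24 | 0.68 | 0.78 | 0.86 |

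Even at f = 0.70, 24 teeth miss the protocol's 0.90 to 0.99 range. For three groups, f = 0.70 means extreme group means 0.70 × √4.5 = 1.48 to 0.70 × √6 = 1.71 SD apart, depending on where the middle mean lies.

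**4. Could the protocol's 95% come from a repeated-measures calculation?** The follow-up schedule in Research Method reads: "contacted for medical checkups at three-month intervals during the first year of the study, and at six-month intervals during the second year", that is at 3, 6, 9, 12, 18 and 24 months. Elsewhere "The goal of the study is to successfully obtain 12-18 months of clinical and radiographic follow-up with at least 24 teeth". Counting a baseline, this gives m = 5 to 7 measurements. The correlation ρ must be assumed. For the time and group-by-time tests, λ = f²·N·m/(1 − ρ). With f = 0.25 and 95% power, the required N is exactly 24 for these values of ρ:

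| m | Group-by-time | Time effect within teeth |
|---|---|---|
| 5 | 0.70–0.74 | 0.62–0.665 |
| 6 | 0.665–0.705 | 0.57–0.625 |
| 7 | 0.63–0.675 | 0.525–0.58 |

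At ρ = 0.5 the group-by-time test needs 39, 36 and 33 teeth for m = 5, 6 and 7. The repeated-measures test between groups, with λ = f²·N·m/(1 + (m − 1)ρ), has only 20% to 35% power at N = 24 for ρ from 0.3 to 0.7.

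A longitudinal origin is therefore possible. However, the time effect within teeth does not compare scaffolds, and the SAP plans neither repeated-measures test.

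**5. The Kruskal-Wallis fallback.** In 100,000 simulated trials with normal data and 8 per group, its power was about 78% at f = 0.70 and 14% at f = 0.25. This is indicative only, because the SAP uses the test when data are not normal.

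**The case against.** The protocol names neither a test nor a metric, so no calculation error is strictly proved. Each document could be reporting a valid output of a different G*Power procedure: a repeated-measures test for 0.25 at 95%, a one-way ANOVA for 0.7 at 80%. On that view this is an unreconciled inconsistency and not wrong arithmetic, and 16% is only one possible reading. It can also be said that f = 0.70 merely fits N = 24, since neither document justifies so large a difference, and that a look-up and some rewording hardly make a serious defect.

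Much of the first part stands. It would be too strong to say that 95% is impossible under every test, and 16% holds only if 0.25 is Cohen's f. But no reading considered brings the protocol's 95% to the test the SAP plans: the other metrics stop at 52% and 65%, and the repeated-measures routes need an unstated correlation and an unplanned analysis. The remark about f = 0.70 is also fair. A statement built on it describes sensitivity and does not justify the sample size clinically. The low cost of the fix does not make the point minor, because the enrolment minimum rests on this calculation.

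**Conclusion.** The concern holds: the power statement is wrong as written for the planned analysis. Two same-dated documents derive 24 teeth from inputs that cannot both give 24 in one test of three independent groups. In the planned one-way ANOVA the protocol's inputs give 16% power against a stated 95% if 0.25 is Cohen's f, and at most 65% on the other metrics tried. The SAP's 80% is supported (82%) provided its d is really f; as a literal d it gives about 20% to 28%.

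The ANOVA figures assume normal data, equal variances, 8 independent teeth per group and alpha 0.05. That the 95% does not describe the planned test does not depend on which calculation lies behind it.

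**What to change.** Keep the minimum of 24 teeth.

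1. Retrieve the saved G*Power output and establish which test and effect-size metric were used.
2. Put one identical power statement in both documents, matched to the planned analysis and naming the outcome.
   - **If the one-way ANOVA stands**, suggested wording, presented as a statement of sensitivity: *24 teeth (8 per group) give 82% power at alpha 0.05 in a one-way ANOVA for Cohen's f = 0.70 (extreme group means about 1.5 to 1.7 SD apart) on [named continuous outcome]; power for f = 0.25 is 16%.* This replaces the protocol's 0.25 and 0.95 and the SAP's symbol d. Say that the 82% belongs to the ANOVA and not to the Kruskal-Wallis fallback.
   - **If a repeated-measures calculation was run**, state its number of measurements and correlation. Then either plan that analysis in the SAP or stop claiming its power for the ANOVA.
3. Reconcile the protocol's sentence on power of 0.90 to 0.99 with the power finally stated.
4. In either case, say that the calculation does not cover the comparison of success rates announced under End Point of the Research.

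The cost is one look-up and wording changes in two documents, with no extra teeth. If the ANOVA stands, the stated sensitivity becomes less favourable. If a repeated-measures analysis is adopted, the SAP gains one model.
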